8.8. Serious Adverse Events Exempt from Expedited Reporting by the Sponsor

All adverse events meeting SAE criteria (see [Section 8.4.1](#) above) must be reported to the Sponsor within 24 hours of when the site is notified of the event. The following refers to Sponsor processing of SAEs, but does not impact Investigator responsibilities for reporting of any SAE.

Potential pre-specified cardiovascular SAEs will be submitted for adjudication to an independent EAC (see [Section 7.8.1](#) for details).

The following potential cardiovascular SAEs will not be subject to expedited reporting by the Sponsor, even if reported as related to study drug by the Investigator, unless and until the event is reviewed by the EAC and found not to meet the specified criteria in the EAC charter for that event type:

1. Cardiovascular deaths.

2. Non-fatal myocardial infarction; hospitalization for chest pain or to rule out myocardial infarction, or other hospitalization due to suspected myocardial ischemia where myocardial infarction needs to be ruled out.
3. Non-fatal stroke; TIA, reversible ischemic neurologic deficit (RIND) or other acute ischemic cerebrovascular event where stroke needs to be ruled out.
4. Hospitalization for unstable angina.

As noted above, SAEs that are confirmed by the EAC as one of the pre-specified cardiovascular endpoints (ie, cardiovascular death, non-fatal myocardial infarction, non-fatal stroke, and hospitalization for unstable angina) in the meta-analysis of cardiovascular safety will not be subject to expedited reporting by the Sponsor to Investigators, Ethics Committees/IRBs and regulatory agencies, regardless of causality. Note that all SAEs, including confirmed adjudicated cardiovascular events, will be reviewed and monitored by an E-DMC unblinded to treatment as part of the overall assessment of safety for ertugliflozin. Based upon their regular review of unblinded safety results, the E-DMC is empowered by the E-DMC charter to make recommendations with regard to trial conduct to assure the continuing appropriate safety of the subjects participating in the study.

If an event submitted for adjudication is determined by the EAC not to meet the endpoint criteria (for the pre-specified events of cardiovascular death, non-fatal myocardial infarction, non-fatal stroke, or hospitalization for unstable angina) in the EAC charter, the event will then be subject to expedited reporting (as appropriate, based upon Investigator assessment of drug relationship). The SAE awareness date in this instance is identified as the date that Pfizer or designee receives notification from the EAC that the event does not meet the endpoint criteria.

9. DATA ANALYSIS/STATISTICAL METHODS

Detailed methodology for summary and statistical analyses of the data collected in this trial will be documented in a Statistical Analysis Plan (SAP), which will be maintained by the sponsor. This document may modify the plans outlined in the protocol; however, any major modifications of the primary endpoint definition and/or its analysis will also be reflected in a protocol amendment.

9.1. Sample Size Determination

With respect to the primary endpoint of reduction in HbA1c from Baseline to Week 26 and assuming an SD of 1.0%,¹¹ the sample size of approximately 600 subjects (200 per arm) provides at least 99% power to detect a difference of 0.5% between each ertugliflozin dose and placebo (and 98% power for detecting this difference for both doses vs placebo) using a two-sided 0.05 alpha level test, allowing for a dropout rate of up to 20%. To control the overall Type I error rate at 0.05 a sequential testing approach will be used across the primary and secondary efficacy endpoints for which hypotheses will be tested, and for the two doses of ertugliflozin.

090177e1848ce2dd\Approved\Approved On: 23-Sep-2013 15:48

The sample size for this trial also provides adequate precision for the comparisons of ertugliflozin versus placebo with respect to the changes in BMD from Baseline to Week 26. In a recent study of another SGLT2 inhibitor (dapagliflozin) in subjects with inadequately controlled T2DM on metformin, the largest variability for the change from baseline in BMD was at the total hip site, with a standard deviation (SD) of approximately 3.3% after 50 weeks.¹³ Assuming that the SD of the change in BMD increases over time, 3.3% was taken as a conservative estimate of the variability at 26 weeks for precision calculations and also to ensure adequate precision for all BMD sites.

Assuming an SD of 3.3% and allowing for a dropout rate of up to 15% at Week 26, the half-width of the 95% confidence interval for the between-treatment difference is expected to be $\pm 0.7\%$ from the point estimate for the overall study population, and also of approximately $\pm 1.0\%$ for the post-menopausal for ≥ 3 years sub-group which will be analyzed separately (approximately 50% of the overall study population). These CI half-widths would be precise enough to rule out clinically relevant changes in BMD, both for the overall study population and the ≥ 3 years post-menopausal subgroup. This is based on changes in BMD that are approximately 50% of the average changes from baseline to Week 80 observed for thiazolidinediones, which are known to be associated with significant bone loss and an increased risk of fracture.¹⁹

BMD data will not be censored at the point of a subject taking glycemic rescue therapy, so the dropout rate assumed for precision calculation (15%) is lower than that assumed for the HbA1c power calculation (20%). However BMD data will be censored at the point of a subject taking BMD rescue therapy.

9.2. Efficacy Analysis

The primary analysis population for efficacy analyses will be the Full Analysis Set (FAS), which is defined separately for each analysis endpoint to include all randomized subjects who have received at least one dose of investigational product and have at least one measurement of the respective endpoint at any time during Phase A of the trial including baseline and post-baseline time points. The post-glycemic rescue therapy data from subjects who require rescue therapy prior to week 26 will be censored from primary and secondary endpoint efficacy analyses.

9.2.1. Analysis of Primary Endpoint

The primary endpoint of HbA1c will be analyzed using a constrained longitudinal data analysis (cLDA) model with the following terms:

- Treatment (categorical),
- Visit (categorical),
- Treatment by visit interaction,
- Menopausal Status randomization stratum.

This model assumes a common mean across treatment groups at baseline and a different mean for each treatment at each of the post-baseline time points. In this model, the response vector consists of baseline and the values observed at each post-baseline time point.¹⁶ Time is treated as a categorical variable so that no restriction is imposed on the trajectory of the means over time. No explicit imputation of missing assessments will be performed. The treatment difference between each dose of ertugliflozin and placebo in terms of mean change from baseline at the primary time point of Week 26 will be estimated and tested from this model using least-squares means and 95% confidence intervals. The two-sided p-value will also be provided for testing the significance of the difference between treatment groups. An unstructured covariance matrix will be used to model the correlation among repeated measurements. The Kenward-Roger adjustment will be used with restricted (or residual) maximum likelihood (REML) to make proper statistical inference.

Sensitivity analyses will be performed to assess the robustness of the primary model. ANCOVA will be conducted utilizing the last observation carried forward as the dependent variable and including fixed factors for treatment (categorical), randomization stratum (categorical), and baseline value (continuous). A per protocol analysis will also be pre-specified in the statistical analysis plan. Descriptive and graphical summaries by treatment group and time point will also be presented. Other additional analyses to explore the robustness of results to regions and other factors will also be performed.

The two primary hypotheses, comparisons of each ertugliflozin dose to placebo will be tested sequentially to control the overall Type I error rate at 0.05. The 15 mg dose will be tested first, and the 5 mg dose will be tested if and only if a statistically significant result is achieved for 15 mg.

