4.3. Randomization Criteria

The randomization will be stratified based on post-menopausal status (as well as geographical region -primarily to facilitate drug supply logistics). Approximately 50% of the population enrolled in the trial will be women who have been post-menopausal for 3 years or more (at least 3 years since their last menstrual period [LMP] or bilateral oophorectomy performed 3 years or more prior to screening), and the randomization will be stratified based on this post-menopausal status. The stratification factor will have 4 levels:

- Men.
- Premenopausal women.
- Women who are perimenopausal or post-menopausal for less than 3 years after LMP or bilateral oophorectomy performed less than 3 years prior to screening,
- Women who are post-menopausal for 3 years or more after LMP or women with a history of bilateral oophorectomy performed 3 years or more prior to screening.

Randomization to the men, premenopausal women, perimenopausal or <3 years post-menopausal women groups will be capped at approximately 50% overall, to ensure approximately 50% of randomized subjects are in the group of women who have been post-menopausal for 3 years or more after LMP, or with a history of bilateral oophorectomy performed 3 years or more prior to screening.

Subjects will be assigned a unique identifier via an Interactive Voice Response System (IVRS) at Screening Visit (S1), which will be retained throughout the duration of their participation in the trial. Subjects who have discontinued a diabetes medication at S2 or needed a change in their metformin dose at S2 or who were not on metformin ≥ 1500 mg/day for ≥ 8 weeks at S2 are required to have an HbA1c measurement at S3 to determine eligibility as defined in the inclusion criteria. These subjects will start the placebo run-in at S3 but can only be randomized on Day 1 (V4) if the S3 HbA1c meets the entry requirement. Subjects will be randomized into the study at V4, provided that they have satisfied all subject eligibility criteria. Eligibility criteria are outlined in [Sections 4.1](#) and [4.2](#) and should be verified at S1, S2 and S3 as applicable. A computer-generated randomization code using the

090177e1848ce2dd\Approved\Approved On: 23-Sep-2013 15:48

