method of random permuted blocks will be utilized to assign on Day 1 (V4) subjects to 1 of the 3 treatment regimens (ertugliflozin 5 mg, ertugliflozin 15 mg, or placebo). The same randomization code will then be used to assign blinded glimepiride/placebo therapy for Phase B.

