9.2.2. Analysis of Secondary Endpoints

The proportion of subjects achieving an HbA1c <7% (53 mmol/mol) at Week 26 will be analyzed using a logistic regression model with terms for treatment (categorical), Baseline HbA1c (continuous). Summary measures from the analysis will include the odds ratio, 95% confidence interval for the odds ratio, and p-value for the comparison of treatment groups.

The secondary endpoints of fasting plasma glucose, body weight, systolic blood pressure and diastolic blood pressure will be analyzed separately by fitting constrained longitudinal data analysis models similar to that used for the primary endpoint. Sitting blood pressure collected in triplicate will be used for assessment of blood pressure as a secondary endpoint.

The secondary efficacy endpoints of FPG, proportion of subjects achieving an HbA1c <7%, body weight, systolic blood pressure and diastolic blood pressure will be tested for each ertugliflozin dose versus placebo using a multiple testing procedure that strongly controls the overall Type I error rate at 0.05. A step-down hierarchical, sequential testing approach will be used, as follows:

| Order | Endpoint (Change from Baseline to Week 26*) | Arm Comparison |
|---|---|------------------------------------|
| 1 | HbA1c | 15 mg ertugliflozin arm to placebo |
| 2 | HbA1c | 5 mg ertugliflozin arm to placebo |
| 3 | FPG | 15 mg ertugliflozin arm to placebo |
| 4 | FPG | 5 mg ertugliflozin arm to placebo |
| 5 | Body Weight | 15 mg ertugliflozin arm to placebo |
| 6 | Body Weight | 5 mg ertugliflozin arm to placebo |
| 7 | HbA1c <7.0% at Wk 26 | 15 mg ertugliflozin arm to placebo |
| 8 | HbA1c <7.0% at Wk 26 | 5 mg ertugliflozin arm to placebo |
| 9 | Systolic BP | 15 mg ertugliflozin arm to placebo |
| 10 | Systolic BP | 5 mg ertugliflozin arm to placebo |
| 11 | Diastolic BP | 15 mg ertugliflozin arm to placebo |
| 12 | Diastolic BP | 5 mg ertugliflozin arm to placebo |
| *Except for HbA1c <7.0% at Wk 26 endpoint | | |

Starting with the first hypothesis, the test will be conducted at a 5% level of significance. If the hypothesis test is significant, then the next hypothesis will be tested at a 5% level of significance. Otherwise, testing ceases within this hierarchy.

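### Region is in no listed model, the HbA1c <7% model has neither randomisation factor, and the cLDA has no stratum-by-visit term: slightly conservative tests, cheap to avoid

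*Combined protocol and SAP*

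**What the plan says.** **Randomisation (Section 4.3).** There are two factors. The first is menopausal status: "The stratification factor will have 4 levels". The second is "geographical region -primarily to facilitate drug supply logistics". Allocation is in blocks: the "method of random permuted blocks will be utilized to assign on Day 1".

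**Primary model (Section 9.2.1).** The cLDA terms are treatment, visit, treatment by visit, and "Menopausal Status randomization stratum". Baseline is part of the outcome: "the response vector consists of baseline and the values observed at each post-baseline time point".

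**Sensitivity and robustness (Section 9.2.1).** The LOCF ANCOVA includes "randomization stratum (categorical), and baseline value (continuous"), without saying which factors make up the stratum. Region appears only in a general promise: "Other additional analyses to explore the robustness of results to regions and other factors will also be performed".

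**Other models.** FPG, body weight and blood pressure follow the primary model's form (Section 9.2.2). BMD lists the same terms as the primary model (Section 9.2.3.1). The HbA1c <7% endpoint "at Week 26 will be analyzed using a logistic regression model with terms for treatment (categorical), Baseline HbA1c (continuous"), with nothing further listed.

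Section 9 leaves detailed methodology to a SAP and calls for a protocol amendment if the primary analysis changes in a major way.

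**The concern.** Stratified blocks make the arms alike on the stratification factors, and this happens whatever the reason for stratifying. If a factor predicts outcome, the balance removes its contribution from the true error of the treatment difference. A model without the factor leaves that contribution in the estimated error. Tests are then conservative and intervals too wide.

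The stratum term needs care. Because baseline is in the response vector, a main effect without a visit interaction imposes one common shift at baseline and at every later visit. It captures a difference in level fully, but a difference in change only in part, and change is the endpoint.

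The stakes are modest. They fall on the secondary tests, which run in a fixed sequence that stops at the first failure (the HbA1c <7% comparisons are seventh and eighth), and on the width of the BMD safety intervals.

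**Working it through.** **The plan's own figures (Section 9.1).** With 200 × 0.80 = 160 per arm, a difference of 0.5 and SD 1.0, the standardised difference is 0.5 / √(2/160) = 4.472. Power is Φ(4.472 − 1.96) = 0.994, against at least 99% stated. For both doses, with correlation 0.5 between the comparisons, power is 0.989, against 98% stated. BMD half-width with 200 × 0.85 = 170 per arm: 1.96 × 3.3 × √(2/170) = 0.702; with 85 per arm, 0.992. The plan states 0.7 and about 1.0.

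**Does the stratum main effect adjust the change?** Large-sample two-visit cLDA, assuming SDs 0.9 and 1.0 and correlation ρ. With the full by-visit term, the Week 26 variance given baseline is v_full = 1 − ρ². An equal stratum shift at both visits leaves no excess under the main effect. A shift at Week 26 only leaves:

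| ρ | SD of shift | v_full | v_planned | R² = 1 − v_full/v_planned |
|---|---|---|---|---|
| 0.4 | 0.2 | 0.840 | 0.864 | 2.7% |
| 0.4 | 0.4 | 0.840 | 0.932 | 9.9% |
| 0.6 | 0.2 | 0.640 | 0.671 | 4.6% |
| 0.6 | 0.4 | 0.640 | 0.760 | 15.8% |

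**Linear models.** Let R² be the share of the planned model's Week 26 error variance that the omitted terms would explain. The documents give no value, so a range is assumed. With k = √(1 − R²):

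- half-width = planned half-width × k
- type I error of the planned test = 2[1 − Φ(1.96/k)], the lowest value, reached if allocation fully balances the omitted factors
- HbA1c power = Φ((4.472 − 1.96)/k) as planned, and Φ(4.472/k − 1.96) with the terms

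| R² | k | BMD, all | BMD, ≥3 years post-menopausal (region only) | Type I error | HbA1c power, planned | HbA1c power, with terms |
|---|---|---|---|---|---|---|
| 0 | 1 | 0.702 | 0.992 | 0.050 | 0.9940 | 0.9940 |
| 0.02 | 0.990 | 0.694 | 0.982 | 0.048 | 0.9944 | 0.9947 |
| 0.05 | 0.975 | 0.684 | 0.967 | 0.044 | 0.9950 | 0.9957 |
| 0.10 | 0.949 | 0.666 | 0.941 | 0.039 | 0.9960 | 0.9971 |

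For an endpoint with 80% power at R² = 0, the same formulas give 80.6% as planned and 82.0% with the terms at R² 0.05, and 81.3% and 84.0% at R² 0.10.

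**cLDA simulation under the null** (480 subjects, blocks of six within four strata by four regions, factors acting on change, 4,000 runs by two doses, Monte Carlo SE about 0.25 points). With the two factors' total share of variance at 0, 2, 7.5 and 15%, the listed model rejected 4.8, 4.6, 4.7 and 3.9%. With both by-visit terms it rejected 4.8, 4.8, 5.4 and 5.1%. Conservatism is clear only at the top of that range.

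**Logistic simulation** (all inputs assumed: 480 subjects, strata 42/4/4/50%, five equal regions, blocks of six, baseline slope −1.0 and SD 0.9, placebo response about 27%, log odds ratio 0.70, 16,000 runs per case, Monte Carlo SE about 0.3 points for power and 0.2 for type I error):

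| Combined logit SD of factors | SE, omitted → included | Power | Type I error |
|---|---|---|---|
| 0 | 0.261 → 0.264 | 77.7 → 78.0% | 4.8 → 5.0% |
| 0.3 | 0.260 → 0.265 | 77.1 → 78.1% | 4.5 → 4.8% |
| 0.6 | 0.257 → 0.270 | 73.5 → 76.2% | 4.3 → 5.0% |

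Adjustment raises the SE here because it targets a larger, conditional odds ratio. The gain is in power, not precision.

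**Sparse levels.** If each of the two smallest strata holds 4, 2 or 1% of 480 subjects (about 19, 10 or 5), the chance that one is empty or has a single outcome is 0.2, 6 or 42%. Pooling the two at 4% each gives power of 78.0, 78.0 and 76.2%, the same to within 0.1 point.

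**The case against.** The strongest defence is that the choice is coherent. Region is stratified for supply reasons, the clinically motivated factor is in the HbA1c and BMD models, regional robustness analyses are promised, and the protocol leaves detail to a SAP. The ANCOVA stratum term could be read to include region. Every harm figure rests on an assumed R² or logit SD, with zero in the range. The type I error values are lower bounds: random loss of 20% of subjects weakens the balance, and 2[1 − Φ(1.96/√(1 − 0.8R²))] gives 0.0455 and 0.041 at R² 0.05 and 0.10 instead of 0.044 and 0.039. In the logistic model, 0.3 points of power appear even at logit SD 0, so that part is not adjustment. A separate simulation put the adjusted logistic model at 5.1 to 5.5% under the null. The fix adds parameters and may need an amendment.

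Much of this stands, and it is why the point is minor. It does not remove it. Blocking balances region whatever the motive, and unspecified robustness analyses do not set the confirmatory p-values or the BMD intervals. Section 9.2.3.1 counts four randomisation strata, which is menopausal status alone, so the ANCOVA term probably omits region, although that is inference. Leaving detail to the SAP is a reason to settle the terms there. The HbA1c <7% model omits even the stratum that the primary and BMD models carry.

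**Conclusion.** The point holds, at minor severity. Reading the terms as listed, the analysis does not fully follow the randomisation. There is no bias and no inflation of type I error, and the primary HbA1c conclusion is not threatened: power is 99.4 to 99.6% as planned and 99.4 to 99.7% with the terms.

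Across assumed R² of 0 to 0.10, linear-model intervals would narrow by 0, 1.0, 2.5 or 5.1%. The BMD half-width stays 0.7 at the plan's rounding, and the subgroup half-width stays 1.0 except at R² 0.10, where it is 0.9. The planned BMD precision still holds, because that calculation assumes no covariate adjustment. The logistic model loses 0.3 to 2.7 points of power under the assumed inputs. If the omitted terms predict nothing, nothing is lost.

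**What to change.** Before unblinding:

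1. Add menopausal stratum by visit, and region with region by visit, to the cLDA models for HbA1c, FPG, body weight, systolic and diastolic blood pressure, and BMD. In BMD subgroups that are a single stratum (men; women at least three years post-menopausal), add only the region terms.
2. Add both factors as main effects to the HbA1c <7% logistic model, and state that the odds ratio is conditional on them.
3. Set in advance a rule for pooling small regions and, if sparse, the two small female strata.
4. State that the stratum term in the sensitivity ANCOVA covers both factors.

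**Cost.** SAP text, plus a protocol amendment if the primary-model change is judged major. No new data are needed. Extra parameters, with about 600 subjects randomised:

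- HbA1c (five time points): 3 × 4 = 12 for stratum by visit, and 5 per additional region
- BMD (two time points): 3, and 2 per additional region
- logistic model: 3, and 1 per additional region

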9.2.2. Analysis of Secondary Endpoints

The proportion of subjects achieving an HbA1c <7% (53 mmol/mol) at Week 26 will be analyzed using a logistic regression model with terms for treatment (categorical), Baseline HbA1c (continuous). Summary measures from the analysis will include the odds ratio, 95% confidence interval for the odds ratio, and p-value for the comparison of treatment groups.

The secondary endpoints of fasting plasma glucose, body weight, systolic blood pressure and diastolic blood pressure will be analyzed separately by fitting constrained longitudinal data analysis models similar to that used for the primary endpoint. Sitting blood pressure collected in triplicate will be used for assessment of blood pressure as a secondary endpoint.

The secondary efficacy endpoints of FPG, proportion of subjects achieving an HbA1c <7%, body weight, systolic blood pressure and diastolic blood pressure will be tested for each ertugliflozin dose versus placebo using a multiple testing procedure that strongly controls the overall Type I error rate at 0.05. A step-down hierarchical, sequential testing approach will be used, as follows:

| Order | Endpoint (Change from Baseline to Week 26*) | Arm Comparison |
|---|---|------------------------------------|
| 1 | HbA1c | 15 mg ertugliflozin arm to placebo |
| 2 | HbA1c | 5 mg ertugliflozin arm to placebo |
| 3 | FPG | 15 mg ertugliflozin arm to placebo |
| 4 | FPG | 5 mg ertugliflozin arm to placebo |
| 5 | Body Weight | 15 mg ertugliflozin arm to placebo |
| 6 | Body Weight | 5 mg ertugliflozin arm to placebo |
| 7 | HbA1c <7.0% at Wk 26 | 15 mg ertugliflozin arm to placebo |
| 8 | HbA1c <7.0% at Wk 26 | 5 mg ertugliflozin arm to placebo |
| 9 | Systolic BP | 15 mg ertugliflozin arm to placebo |
| 10 | Systolic BP | 5 mg ertugliflozin arm to placebo |
| 11 | Diastolic BP | 15 mg ertugliflozin arm to placebo |
| 12 | Diastolic BP | 5 mg ertugliflozin arm to placebo |
| *Except for HbA1c <7.0% at Wk 26 endpoint | | |

Starting with the first hypothesis, the test will be conducted at a 5% level of significance. If the hypothesis test is significant, then the next hypothesis will be tested at a 5% level of significance. Otherwise, testing ceases within this hierarchy.

